15. BIBLIOGRAPHY							

EXPERIMENTAL SCHEMA

Figure 1: Standardized treatment protocol including study inclusion criteria and discharge checklist.

Discharge

Follow up within 30

days in clinic or via

phone or mail

PROTOCOL SIGNATURE

I confirm that I have read and understood this protocol, and I will conduct the study as outlined herein and according to the ethical principles stated in the latest version of the Declaration of Helsinki, the applicable ICH guidelines for good clinical practice, and the applicable laws and regulations of the federal government. I will promptly submit the protocol to the IRB for review and approval. Once the protocol has been approved by the IRB, I understand that any modifications made during the course of the study must first be approved by the IRB prior to implementation except when such modification is made to remove an immediate hazard to the subject.

I will provide copies of the protocol and all pertinent information to all individuals responsible to me who assist in the conduct of this study. I will discuss this material with them to ensure that they are fully informed regarding the study treatment, the conduct of the study, and the obligations of confidentiality.

Signature of Principal Investigator

Date

[name]

Principal Investigator Name (Print)

Johns Hopkins All Children's Hospital

Name of Institution

STUDY SUMMARY

Title	Antibiotic Instillation in Acute Complex Appendicitis for
	Prevention of Deep Space Surgical Site Infections
Short Title	Antibiotic Instillation in Appendicitis
IND	IND
Phase	Pilot Phase 2
Design	Randomized single blind control study
Study Duration	1 year
Study Center(s)	Single-center
Objectives	The primary objective is to evaluate the feasibility and safety of the use of antibiotic instillation in the treatment of complex acute appendicitis measured by enrollment rates and ability to complete all study tasks. Secondary objectives are to examine the rate of intra-abdominal abscess formation and post-operative length of stay following treatment of complex appendicitis in the setting of appendectomy with intra-operative suction alone compared to suction with intra-peritoneal antibiotic instillation
Number of Participants	A total of 36 patients will be randomized to two groups in this pilot study
Diagnosis and Main Eligibility Criteria	Intraoperative diagnosis of complex appendicitis defined by: a visible hole in the appendix, extra-luminal fecalith, diffuse fibropurulent exudate (outside the right lower quadrant (RLQ)/pelvis) or presence of intra-peritoneal abscess
Study Product, Dose, Route, Regimen	Ceftriaxone, >20kg (1g in 9ml of 0.9% normal saline), intraperitoneal instillation given once following appendectomy, and aspiration of excess intra-peritoneal fluid
Duration of Administration	A one-time dose of intra-peritoneal ceftriaxone solution following appendectomy
Reference Therapy	Standard of care is intra-peritoneal aspiration alone, or irrigation of the peritoneal cavity with or without antibiotic in the irrigant fluid.
Statistical Methodology	Descriptive statistics will be used to summarize the results. Continuous variables will be summarized using means and standard deviation or median and range as appropriate. Categorical variables will be summarized using counts and percentages. Data will be presented using tables and figures

1 OBJECTIVES

1.1.1 Primary objective

To evaluate the feasibility and safety of the use of antibiotic solution instillation following intraoperative diagnosis of complex appendicitis. We will determine feasibility by the percentage of eligible participants who (1) agree to participate, and (2) complete all intervention sessions and measurement time points. Safety will be evaluated by adverse events associated with the use of intra-peritoneal antibiotic instillation for the treatment of peritonitis caused by complex appendicitis.

1.1.2 Secondary objectives

- A. To evaluate preliminary efficacy of antibiotic solution instillation following diagnosis of complex appendicitis.
- B. To compare the following outcomes between patients who receive or do not receive antibiotic solution instillation following diagnosis of complicated appendicitis: operative time, length of stay, post-operative antibiotic use, post-operative pain medication use, need for post-operative imaging, readmission rates, and the development of intra-peritoneal abscess requiring percutaneous aspiration and/or drainage within 30-days following appendectomy.

2 BACKGROUND AND RATIONALE

Appendicitis is the most common abdominal surgical emergency in children, affecting approximately 75,000 children a year.[1, 2] Mitigating the associated morbidities of this disease process is of paramount concern to the pediatric surgeon.[1] In complicated or complex appendicitis, the infectious process is noted to have progressed beyond the confines of the appendix, which leads to purulent fluid in the intra-peritoneal space (diffuse exudate outside of the right lower quadrant (RLQ)/pelvis), a visible hole (perforation) of the appendix, an extra-luminal fecalith, or an intra-peritoneal abscess. Complex appendicitis occurs in up to 20% of all cases of appendicitis and is associated with a much higher morbidity and mortality than its simple counterpart.[1, 3-5]

The ensuing systemic response from complex appendicitis has a significant impact on the patient and their families. Complex appendicitis results in significant morbidity, with increased rates of intra-peritoneal abscess formation, and surgical site infections, as well as increased length of stay. [6, 7] The increased inflammation and bacterial insult can result in urinary retention, diarrhea, increased pain, and a high incidence of deep organ space infection. [6] In the peritoneal space, infection can progress to form an intra-abdominal abscess, which is treated with intravenous antibiotics and often percutaneous or operative drainage. All of these factors in combination with the increased level of systemic insult experienced by the patient, correlate with longer and more costly hospital stays, increased need for advanced imaging leading to more radiation exposure, prolonged antibiotic use, and increased discomfort and generalized malaise, more time away from school, work, and home.

Current management strategies for intra-operatively diagnosed complex appendicitis include appendectomy with aspiration of infected intra-peritoneal fluid followed by continued post-operative treatment with intravenous or oral antibiotic therapy.[8] Previous studies have not seen dramatic

improvements with antibiotic irrigation, large volume irrigation, or prophylactic intra-peritoneal drain use to prevent intra-abdominal abscess formation.[9-18] As such, the search continues to find an answer to the high rate of deep space infection associated with complex appendicitis, which can be as high as 45%.[5, 19]

Interventions to counter these negative effects currently focus on the aftermath of an intraabdominal abscess and how to manage it once it has been identified. Previous studies have investigated the use of peritoneal irrigation solutions (with or without antibiotics) at the time of surgery, in hopes of decreasing intra-abdominal abscess rates and length of stay following appendectomy, but these studies did not show any significant improvement in abscess rates after irrigation compared to aspiration alone.[5, 18, 20] These previous studies may not have observed an improvement in post-operative complications given that they did not allow for the antibiotic solution to remain in the intraperitoneal space.

The current pilot project focuses on assessing the feasibility of using antibiotic instillation to prevent deep organ space surgical site infection, which would be a significant improvement to the existing standard of care. Currently there is no literature that describes utilizing antibiotic instillation in the treatment of complicated appendicitis, thus this pilot study will provide important feasibility data prior to instituting a large multicenter trial. Pending feasibility of our pilot study, our project will further study the length of stay, and potential prevention of intra-abdominal abscess. The outcomes of this limited efficacy testing will be an important initial step to designing a larger, multicenter trial which is powered to show improved postoperative outcomes with decreased postoperative abscess formation in complicated appendicitis.

We believe that after appendectomy and removal of the nidus of disease, the post-operative field would benefit from treatment with an antibiotic instillation, a solution placed in the peritoneal cavity in direct contact with the contaminated surfaces. By leaving the antibiotic solution in place at time of closure, the contaminated areas are topically treated with prolonged exposure to the bactericidal effects of ceftriaxone (). This technique will give appropriate temporal contact of the medication to the bacteria, allowing for better dispersion, and optimized efficacy.

In patients with peritoneal dialysis catheters, infection of these catheters can lead to peritonitis, or inflammation of the peritoneal cavity, which, in turn can progress to sepsis. Peritonitis associated with infected peritoneal dialysis catheters is treated with antibiotic instillation into the peritoneal cavity with demonstrated success and is currently considered the standard of care treatment.[21-24] Intra-peritoneal antibiotic instillation is the current standard of care for treatment of peritonitis associated with PD catheters.[25] Given that intra-peritoneal antibiotic instillation is the standard of care for PD catheter associated peritonitis, it should also be safe to use for any type of peritonitis, and in this case, peritonitis due to complicated appendicitis.

Recently, the treatment regimens have shifted away from continuous use of antibiotic instillations during PD sessions and have moved towards intermittent antibiotic instillations with daily dosing.[26, 27] The International Society for Peritoneal Dialysis (ISPD) recommends at least a 6 hour dwell time for intermittent antibiotic instillation to allow for adequate absorption.[25] The ISPD guidelines also suggest that cephalosporins be administered on a daily intermittent basis, or continuously (with each exchange), as there is no significant difference in peritonitis treatment outcomes with these dosing regimens.[25] Given the broad coverage, we believe that the intraperitoneal use of ceftriaxone will lead to better treatment of complex appendicitis and potentially decreased incidence of intra-abdominal abscesses. This aligns with typical treatment strategies for peritonitis associated with PD catheters, which have been successful.[22, 26, 28] Second or third generation cephalosporins are the standard of care antibiotics used pre-operatively prior to an appendectomy. At our institution pre-operative intravenous (IV) ceftriaxone (50mg/kg/day,

maximum 2g daily) and metronidazole (30mg/kg/day) therapy is used as pre-operative antibiotic treatment prior to pediatric appendectomy. [29] Intravenous ceftriaxone (50mg/kg/day, maximum 2g daily) and metronidazole(30mg/kg/day) is given post-operatively following the diagnosis of complicated appendicitis for a minimum of 48 hours following surgery. The maximum daily dosage of intravenous ceftriaxone administered during the conduct of the study will be 2g. We anticipate that the intra-peritoneal instillation of ceftriaxone will decrease the length of stay and decrease the post-operative development of deep organ space surgical site infection in patients with complicated appendicitis due to the longer contact with the inflamed area of the RLQ following removal of the nidus of infection, or the appendix. A small volume of instilled ceftriaxone (~10ml solution total) will be used so as not to instill a significant amount of additional fluid into the peritoneal cavity.

The idea of surgical source control paired with direct antibiotic instillation and application to the area of infection is an innovative approach to the traditional treatment scheme of complicated appendicitis which could be instrumental in decreasing post-operative complications. Antibiotic instillation into the peritoneal cavity after appendectomy gives maximal contact time between the antibiotic and the bacteria in question, and leads to elevated local antibiotic concentration. To our knowledge, no study has ever sought to use antibiotics as a topical, retained solution in an infected peritoneum due to complicated appendicitis. We believe that by applying the antibiotics directly to site of highest bacterial presence and allowing the medication to remain in contact with this field. that the overall response will be better bacterial control and decreased rates of intra-abdominal abscess formation and complications. This is a new concept and has not vet been reported in pediatric patients with complicated appendicitis. The long-term goal of the study is to compare incidence of postoperative deep organ space infection following our standard of care (aspiration of intra-peritoneal infected fluid only) compared with aspiration of intra-peritoneal infected fluid followed by antibiotic instillation of ceftriaxone. This pilot study will evaluate the feasibility of this novel approach and will yield the necessary preliminary data for a larger study to evaluate the effectiveness of this treatment scheme

2.1 Benefit / Risk Assessment

Appendicitis is one of the most common surgical diagnoses in the pediatric population and the most common surgical emergency in children.[1, 2] In complex appendicitis, the sequelae have progressed beyond the confines of the organ, and have led to purulent fluid in the intra-abdominal space, spillage of intestinal contents, or gross perforation of the appendix. Complicated appendicitis occurs in up to 20% of cases and is associated with a much higher morbidity and mortality. [5] Previous studies have shown that local treatment of peritonitis associated with PD catheters with intra-peritoneal antibiotics has had significant improvement of outcomes.[22, 23, 26, 28] The intra-peritoneal route is preferable as compared to oral and intravenous antibiotic administration due to elevated local levels of the antibiotic above the minimum inhibitory concentration while avoiding venipuncture and systemic side effects.[25, 26] There is minimal risk associated with involvement in this study given that we will be screening for any history of allergies to penicillin or cephalosporins, and excluding these patients. Ceftriaxone is commercially available, has a low risk profile, and is generally well tolerated with minimal side effects.

Our treatment period will include a one-time intra-operative dose of intra-peritoneal ceftriaxone. Typical dosing strategies for intra-peritoneal ceftriaxone administration occur on a daily basis, so our treatment period will also include the 24 hours following intra-peritoneal administration of ceftriaxone. All patients diagnosed with acute complicated appendicitis intra-operatively, and entered into our study, will also receive a minimum 48 hours of intravenous antibiotics as an inpatient, allowing for continued observation. We will be treating pediatric patients who are intra-

operatively diagnosed with complex appendicitis, as defined by any of the following: visible hole in the appendix, extra-luminal fecalith, diffuse fibropurulent exudate outside the RLQ/pelvis, or intraperitoneal abscess. All patients will have been admitted to Johns Hopkins All Children's Hospital with a diagnosis of acute appendicitis prior to surgical intervention. Patients will then be randomized once diagnosed with complex appendicitis intra-operatively. Patients with allergies to penicillin or cephalosporins will be excluded pre-operatively, as well as patients who do not meet the weight requirement, are pregnant, have a history of neurological conditions such as encephalopathy, seizures, myoclonus and non-convulsive status epilepticus, have a known inability to complete a 30day postoperative follow up, are being treated non-operatively, and those who have been intra-operatively diagnosed with simple appendicitis.

3 DRUG INFORMATION

Ceftriaxone is a sterile, semisynthetic, broad-spectrum cephalosporin antibiotic for intravenous, intramuscular, or intra-peritoneal administration.

Ceftriaxone sodium is (6R,7R)-7-[2-(2Amino-4-thiazolyl)glyoxylamido]-8-oxo-3-[[(1,2,5,6-tetrahydro-2-methyl-5,6-dioxo-*as*triazin-3-yl)thio]methyl]-5-thia-1-azabicyclo[4.2.0]oct-2-ene-2-carboxylic acid, 7²-(*Z*)(*O*-methyloxime), disodium salt, sesquaterhydrate. The chemical formula of ceftriaxone sodium is C18H16N8Na2O7S3•3.5H2O.

Ceftriaxone is a white powder, which is soluble in water. In this study ceftriaxone crystalline powder will be dissolved in 0.9% sodium chloride solution prior to intra-peritoneal instillation.

1g of ceftriaxone will dissolve in 9ml of 0.9% of sodium chloride solution, and when fully withdrawn should result in a total volume of just about 10ml (9.8ml) for intra-peritoneal instillation.

4 STUDY DESIGN

This is a Prospective Randomized Open with Blinding of Endpoint (PROBE) pilot phase 2 study to evaluate the feasibility and safety of the use of antibiotic instillation in the treatment of complex acute appendicitis. All children equal to or greater than 20kg diagnosed with acute appendicitis and undergoing urgent appendectomy will be approached for enrollment for this study. As there is poor pre-operative diagnostic accuracy for simple versus complex appendicitis, all eligible patients presenting with acute appendicitis and their families will be approached for consent. Intra-operative assessment will diagnose complex appendicitis. Complex appendicitis will be defined as presence of any of the following: visible hole in the appendix, extra-luminal fecalith, diffuse fibropurulent exudate outside the right lower quadrant (RLQ)/pelvis, or intraperitoneal abscess. Patients will be excluded if they undergo non-operative management of appendicitis, do not undergo appendectomy at the time of operation, weigh less than 20kg, are pregnant, are unable to complete a 30day postoperative follow up, have impaired renal function (CrCl <15mL/min), have a history of neurological conditions (such as encephalopathy, seizures, myoclonus, and nonconvulsive status epilepticus), or are allergic to penicillin or cephalosporins that prohibit the use of the antibiotic intra-peritoneal instillation. Patients with a history of anaphylactic reactions to penicillin or cephalosporins will be excluded from this study. Patients with a penicillin allergy who have previously received IV cephalosporins without allergic reaction will be considered for inclusion in this study.

Study participants will be randomized in a 1:1 ratio using permuted blocks of 4 and 6 using a computer-generated randomization scheme. The treatment category assignments will be placed in consecutive numbered envelopes concealed from study staff until randomization. In the operating room, once the patient is diagnosed with complicated appendicitis, then the next sequential envelope will be opened and the patient will be assigned to that treatment arm. The surgeon and team administering the treatment will not be blinded; however, patients, their families, and hospital caregivers outside of the operating room will be blinded to the treatment. Post-operative protocols will be the same for both groups and includes continuation of intravenous antibiotics (Study Schema, and Fig 1). Once complex appendicitis is diagnosed, and a successful appendectomy occurs, then the patient will be transitioned to intravenous ceftriaxone (50mg/kg/day, maximum 2g daily) and metronidazole (30mg/kg/day) post-operatively. Both study groups will receive a minimum additional 48 hours of intravenous ceftriaxone and metronidazole, as per our weight based current standard of care. Patient status and post-operative recovery back to baseline will dictate discharge or continued hospitalization. Pending their clinical course, patients will be either transitioned to broadspectrum oral antibiotics or continued on intravenous ceftriaxone and metronidazole until their discharge from the hospital. Our standardized discharge criteria includes: temperature less than 38.5°C for the previous 24 hours, improved abdominal pain without the use of narcotics, and tolerance of enteral intake. Once these criteria have been met, and at the surgeon's discretion, the patient will be discharged home with routine follow-up (either a clinic visit, telemedicine visit, or a phone call) within 30 days after surgery.

If the patient remains hospitalized on post-operative day 7 (plus or minus 1 day) related to postoperative care of complicated appendicitis, and does not meet discharge criteria as listed, then they will undergo subsequent imaging studies (abdominal ultrasound or CT abdomen-pelvis) to evaluate for intra-abdominal abscess or phlegmon. If patients are found to have an abscess or phlegmon, they will continue to receive ongoing antibiotic treatment with or without percutaneous aspiration and/or drainage at the discretion of the surgeon and interventional radiologist.

Patients will undergo telephone, telemedicine visit, or in-person clinic follow-up within 30days of their discharge following their appendectomy. If patients present with symptoms at these checks or independently present to an emergency department, they will undergo routine evaluation and imaging as clinically indicated. Other parameters that will be tracked include development of superficial or deep surgical site infection, inpatient pain scores, inpatient pain medication use, and post-operative length of stay.

An independent clinical endpoint committee will be formed to evaluate for study related complications and endpoints. For consistency and future ease of a prospective multicenter trial, definitions of intraoperative findings of complicated appendicitis, postoperative percutaneous drainage or aspiration of intraperitoneal fluid collection, surgical site infection, postoperative sepsis, readmission and/or reoperation will be reported according to the National Surgical Quality Improvement Program Pediatric Operations Manual, January 2022 edition. [31]

We will evaluate patient retention and recruitment along with the process of instilling antibiotic solution into the intra-peritoneal space in this feasibility study. We will primarily focus on recruitment, enrollment, and retention rates in this pilot study. We will also evaluate patient outcomes associated with intra-peritoneal instillation of antibiotics to determine not only postoperative complication rates, but also length of stay, pain scores, pain medication use, superficial surgical site infections, and adverse events related to the antibiotic instillation. Patients and their families will be blinded to their randomized treatment groups, and will be followed for 30 days following appendectomy.

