7 ANTIBIOTIC INSTILLATION INTERVENTION PLAN

7.1 Intervention Schedule

All patients equal to or greater than 20kg presenting to Johns Hopkins All Children's Hospital with a diagnosis of acute appendicitis and are scheduled to undergo urgent appendectomy will be approached for participation in this study. Intra-operatively their eligibility to participate in the study will be determined. If complex appendicitis is found intra-operatively then the patient will be randomized into the control group (standard of care arm with intra-peritoneal fluid aspiration only), or the study group (intra-peritoneal fluid aspiration and antibiotic solution instillation). Antibiotic instillation will be introduced into the RLQ/pelvis after the appendectomy is completed and all intra-peritoneal fluid is aspirated. Ceftriaxone solution will be used depending on availability and pharmacy stock for use at Johns Hopkins All Children's Hospital. The ceftriaxone powder (1g) will be dissolved in 9ml of sterile normal saline. The entire contents of reconstituted powder will be fully withdrawn for a total instillation volume of 10ml. This fluid will then be instilled and left to dwell in the area of the peritoneal cavity where the appendix was removed.

Intervention

Standard of Care (Control group)/ARM A Intra-operative aspiration of intra-peritoneal fluid after successful appendectomy.

Standard of Care and Antibiotic instillation (Study group)/ARM B Intra-operative aspiration of intra-peritoneal fluid after successful appendectomy and subsequent instillation of 10ml of intra-peritoneal ceftriaxone (1g)

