10 STUDY PROCEDURES

Screening:

Informed Consent

Pre-op Physical exam: Height, weight, abdominal exam

Review of medical history/baseline symptoms including pain score

Pre-op Vitals: heart rate, blood pressure, respiratory rate, pulse oximetry, temperature

Pre-op pain score

Pre-op Labs: CBC w/diff, pregnancy test if warranted

Pre-op imaging: Ultrasound or CT scan

Surgery:

Successful appendectomy will be defined as removal of the appendix and appropriate closure of the cecum.

After successful appendectomy and identification of complex appendicitis, the patient will be randomized into the standard of care arm, or the standard of care with antibiotic instillation arm.

Post-operative monitoring:

Post-operative inpatient Physical exam: abdominal exam

Post-operative inpatient Vitals: heart rate, blood pressure, respiratory rate, pulse oximetry,

- temperature
- Post-operative pain score

Post-operative Inpatient Labs: CBC w/diff if the patient remains hospitalized and is deemed clinically necessary by the surgeon

Post-operative imaging: will occur on POD7 (+/- 1 day) if the patient is still hospitalized and continues to have severe or recurrent abdominal pain, is unable to tolerate a diet, was febrile within the last 24 hours and if clinically warranted has a recent CBC with an elevated WBC.

Follow-up appointment:

Outpatient follow up Physical exam: abdominal exam

Outpatient follow up Vitals: heart rate, blood pressure, respiratory rate, pulse oximetry, temperature Pain score

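### The randomization trigger is not fixed relative to appendectomy and aspiration, so an unblinded surgeon may know the arm during steps common to both arms

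*Combined protocol and SAP*

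**What the plan says.** Four sections of the combined protocol and SAP state when a patient is randomized.

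- Section 4 (Study Design): "once the patient is diagnosed with complicated appendicitis, then the next sequential envelope will be opened".
- Section 2.1 (Benefit / Risk Assessment): "Patients will then be randomized once diagnosed with complex appendicitis intra-operatively".
- Section 7.1 (Intervention Schedule): "If complex appendicitis is found intra-operatively then the patient will be randomized into the control group".
- Section 10 (Study Procedures, Surgery): "After successful appendectomy and identification of complex appendicitis, the patient will be randomized into the standard of care arm". The same section gives the definition: "Successful appendectomy will be defined as removal of the appendix and appropriate closure of the cecum".

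Other statements bear on the timing. Section 4 says "The surgeon and team administering the treatment will not be blinded". It also excludes patients who "do not undergo appendectomy at the time of operation", a criterion that the numbered list in Section 5.2 does not repeat. Section 7.1 places aspiration after successful appendectomy in both arms, and instillation in Arm B after all fluid has been aspirated. Section 1.1.2 lists the between-arm comparisons, among them "operative time, length of stay, post-operative antibiotic use" and intra-peritoneal abscess requiring aspiration or drainage. Section 12 defines the modified intention-to-treat set as patients who were randomized and received surgery. It expects fewer than 1% to switch arm during surgery and about the same not to complete it.

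**The concern.** Up to the moment of instillation the two arms are meant to be treated identically. If the surgeon learns the arm before the shared steps are finished, that knowledge can influence how they are done, for example how long the operation takes or how thoroughly fluid is cleared. Operative time is itself a listed comparison, and completeness of aspiration could plausibly affect abscess. Blinding the family and ward staff, and using an independent endpoint committee, does not correct differences that arise inside the operating room.

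The second issue is the denominator. If the envelope is opened at diagnosis and no appendectomy follows, the patient has been randomized and then meets a Section 4 exclusion. If it is opened after appendectomy, this cannot happen. The pilot is meant to refine procedures for a larger trial, so the trigger is worth settling now.

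**Working it through.** The plan states no figure on this point, so the main check sets the texts side by side.

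| Section | Condition for randomization | Could open before appendectomy? | Could open before aspiration? |
|---|---|---|---|
| 2.1 | Intra-operative diagnosis | Yes | Yes |
| 4 | Intra-operative diagnosis | Yes | Yes |
| 7.1 | Intra-operative finding | Yes | Yes |
| 10 | Diagnosis and successful appendectomy | No | Yes |

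The defining findings (a hole in the appendix, an extra-luminal fecalith, diffuse exudate, an abscess) can be visible before the appendix is removed, so the first three rows describe a practice that could really occur. Section 10's definition of success requires the appendix out and the cecum closed, which comes later than diagnosis. Section 7.1 puts aspiration after that, so the Section 10 rule does not protect the aspiration step. No section reconciles the triggers. Section 12's allowance for randomized patients who do not complete surgery fits randomization before the operation is finished.

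**Scale of post-randomization non-completion.** Inputs: n = 36 (Section 12, sample size) and the rate p, with the plan's figure of less than 1% taken as an upper bound. Expected number = 36 × p; chance of at least one = 1 − (1 − p)^36.

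| p | Expected patients | Chance of at least one |
|---|---|---|
| 0.5% | 0.18 | 17% |
| 1% | 0.36 | 30% |
| 2% (arm switches plus non-completions, each at 1%) | 0.72 | 52% |

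The relevant row for uncompleted surgery is at most the second. It also bounds the exclusion for no appendectomy, provided such cases are counted among the uncompleted surgeries.

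**Operative time.** With 18 per arm, the standard error of a difference in means is SD × √(2/18) = SD/3. The documents give no SD. If it were 15 to 20 minutes (an assumption), the standard error would be 5.0 to 6.7 minutes. This describes the precision of the comparison. It says nothing about how far behaviour would shift, for which the documents offer no input.

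**The case against.** The strongest reply is that the sections are compatible. Section 4 does not say that the envelope is opened immediately on diagnosis or before the appendix is removed. Opening it after both diagnosis and appendectomy satisfies all four sections, and Section 10, as the procedural section, can be read as the more specific rule. This stands. A reader might infer that the sections cannot all be followed, or that Section 4 requires early opening; the text supports neither. What remains is that a surgeon who opens at diagnosis complies with three sections and breaches the fourth.

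Second, exposure during aspiration does not come from the discrepancy, because Section 10 alone leaves it in place. This also stands, and it is why adopting Section 10's wording is not enough.

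Third, the stakes are limited. The trial is an openly declared PROBE pilot, the secondary analyses are exploratory and unpowered, and the feasibility measures (agreement to participate and completion) are not shown to be affected. Section 12 also deals with non-completers in its analysis sets. This lowers the priority. However, accepting an unblinded surgeon does not require that the surgeon learn the arm before the shared steps are done.

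Fourth, late opening is not free. In Arm B the powder must then be fetched from the OR Pyxis, mixed and transferred sterilely (Sections 7.2.1 and 7.2.2), and any wait falls in that arm only and lengthens operative time. The documents give no preparation time, so the size is unknown. This is a real downside and has to be weighed.

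**Conclusion.** The point holds as an unreconciled trigger that permits, but does not oblige, early knowledge of the arm. The main consequence is possible performance bias in operative time and abscess, both exploratory outcomes. Post-randomization exclusion is a minor consequence: 0.36 expected patients at the 1% bound, with a 30% chance of at least one.

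The size of the behavioural effect cannot be derived. A reader might infer from the standard-error calculation that a shift of about 5 minutes would match the whole sampling error. That does not follow. Both the SD and the shift would be assumptions, and 5 minutes would be only 0.75 to 1.0 standard errors (5/6.7 to 5/5.0), inside the 95% interval half-width of about 10 to 14 minutes. Operative time also differs between arms by design, because Arm B adds an instillation step.

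The change is still worth making. It removes an avoidable source of bias and avoids exclusions for no appendectomy after randomization, without altering the treatment sequence in Section 7.1.

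**What to change.** State one trigger in Sections 2.1, 4, 7.1 and 10: the next envelope is opened only after appendectomy is complete and intra-peritoneal fluid has been aspirated, immediately before the point at which instillation would occur.

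Record the time of opening on the case report form, and report operative time before and after randomization separately. The first part cannot be influenced by the allocation and serves as a balance check. The second contains the instillation step and any preparation wait.

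The cost is a wording amendment and one time field, with no added patients or procedures. The downside is a possible short drug-preparation wait in Arm B only, which the time stamp makes visible. Section 8.2 starts serious adverse event collection at randomization, so the amendment would also fix when that window opens and should say so. Section 8.1 already collects adverse events from the operative date in both arms.
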